7.4.4 Return or Destruction of Study Drug

Duvelisib

At each cycle, patients will return any unused duvelisib. Blister packs with unused duvelisib will have their contents destroyed on site per investigational pharmacy procedures

Nivolumab

Nivolumab is regularly stocked at the UPMC Hillman Cancer Center and Winship Cancer Institute and managed according to current pharmacy protocols.

7.5 Treatment Regimen

Duvelisib

Duvelisib is available in 15mg and 25mg dose capsules. Based on information provided in the Investigators Brochure from SecuraBio, in Phase I trials with duvelisib as monotherapy for lymphoma, the maximum tolerated dose of duvelisib was 75mg BID²⁰. After further evaluation 25mg BID was chosen to be the preferred therapeutic dose in an effort to minimize toxicity without compromising efficacy. Given that duvelisib acts primarily as an immunomodulator, as opposed to being directly cytotoxic to tumor, doses were chosen to maximize T cell proliferation according to pre-clinical data²¹. These data suggest that doses lower than even 25mg BID may result in serum drug concentrations able to optimize T cell proliferation. Thus, doses lower than 25mg BID may be ideal for both maximizing immune changes in the TME and reducing patient toxicities. If significant toxicity is noted in the first 3 patients of each/any dose level, subsequent patients may be treated with a 2 week lead-in of duvelisib as monotherapy prior to the addition of nivolumab.

Dosing for the dose escalation phase will be as follows:

Table 7.5 Duvelisib Dose levels

Dose Level	Duvelisib Dose
Level I	15mg Daily
Level II	25mg Daily
Level III	25mg BID

Nivolumab

Nivolumab will be administered at a flat dose of 240mg every 2 weeks for the first 4 cycles, thereafter it then may be switched to 480mg every 4 weeks (+/- 1 week allowed without study deviation) if deemed appropriate by the treating physician in consultation with a given patient and his/her caretakers. Patients changed to the every 4 weeks schedule for nivolumab will continue to undergo close monitoring by the study team for potential toxicities, as deemed necessary and appropriate by the treating physician.

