Main Inclusion and Exclusion Criteria	
Inclusion criteria: Men and women 18 years of age or older with unresectable stage III or stage IV melanoma by AJCC 8th edition who have progressed on anti-PD1 therapy after a minimum of 12 weeks of therapy.
 
Exclusion criteria: Patients with known or suspected symptomatic or progressive CNS metastases; patients with treated CNS disease who are stable on repeat imaging at 2-4 weeks post SRS and neurologically stable are allowed. Patients with active autoimmune disease requiring treatment and patients with uveal or mucosal melanoma are not eligible. Patients with uncontrolled cardiovascular, pulmonary, and certain infectious disease are also excluded.

Investigational Product	
Duvelisib is an oral medication that will be administered in doses from 15mg once a day to 25mg BID for dose finding studies.
 
Nivolumab is supplied as a 240mg/24 mL formulation to be administered as an IV infusion at 240mg every 2 weeks, and if tolerated, potentially changed to 480mg once every 4 weeks.

Duration of administration	Both duvelisib and nivolumab will be administered in 4-week cycles until progression of disease, unacceptable toxicity, or 1 year, whichever is longer.
Reference therapy	For patients who have progressed on immunotherapy and targeted agents, there is no current standard of care ¹ and clinical trials are the recommended option.
Correlative studies	Patients will have peripheral blood draw and tumor biopsy performed at baseline and after 12 weeks of treatment in both phases of the trial. For the phase I cohort, changes in immune cell populations, particularly CD8+ T cell proliferation, will be used to measure the immunomodulatory effect of increasing doses of duvelisib. Additional studies are planned to characterize T cell phenotype, function, and metabolism as well to evaluate expression of genes involved in autoimmunity and inflammation and to correlate with toxicity. Correlative studies will be used along with toxicity data to inform the phase II dose. Ideally, the dose chosen will have a potent anti-tumor immune profile such as high CD8+ T effector cells, low T regulatory cells, low myeloid-derived suppressor cells.

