4.4.1 Duration of Follow Up and Retreatment

The period of acute toxicity and DLT evaluation is 28 days. Beyond that, AEs that arise while on treatment and within 4 weeks (+ 2 weeks) after discontinuation of treatment will be considered late toxicities

Patients will be evaluated by the treating physician after trial discontinuation, regardless of reason for discontinuation. Patients will be seen for an additional visit 4 weeks (+ 2 weeks) after study discontinuation to evaluate for additional adverse events and will continue to be followed until all adverse events have resolved or stabilized. The investigator and treating physician are responsible to ensure, within reason, that the patients receive appropriate treatment for their malignancy after trial discontinuation. Patients may be contacted for survival follow-up for up to 5 years. Survival follow-up will be performed approximately every 3 months. Patients terminated from the trial for adverse events will be followed until resolution or stabilization of the adverse event. Patients will have regular lab work and need documentation of CD4 T-cell subset >200 cells/ μ L prior to stopping PJP prophylaxis. We anticipate 3 years of data collection to determine duration of response.

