8.1 Dose Limiting Toxicities

Acute dose limiting toxicities (DLTs) are defined as any of the following AEs and laboratory abnormalities considered possibly, probably, or definitely related to study treatment that occur any time from the initial dose of duvelisib in combination with nivolumab through day 28 of treatment. Toxicities occurring from day 29 through 28 days after completion of treatment will be considered late toxicities. Only acute DLTs will be considered for decisions to continue enrollment at the current dose level or proceed to the next dose level. Acute and late toxicities will be considered when deciding on the RP2D and will be discussed in monthly Data Safety Monitoring Board (DSMB) meetings. See Section 15.0 for further details.

Severity of adverse events will be graded by National Cancer Institute Common Terminology Criteria for Adverse Events version 5.0 (CTCAE v5.0). A goal of $\leq 33\%$ DLTs at each dose level will be considered acceptable.

Whenever possible, biopsies are recommended if they can be done safely to help determine between immune-related and other etiologies of toxicity, particularly for rash and colitis. Biopsies for elevated liver enzymes and/or for pneumonitis should be considered if deemed feasible and safe in the context of risk:benefit evaluation. General criteria for consideration of biopsy:

- Diarrhea/colitis
 - Biopsy proven grade ≥ 3 immune-related colitis
 - Diarrhea of grade ≥ 3 that does not respond to treatment with steroids within 5 days
- Pneumonitis
 - Immune-related pneumonitis grade ≥ 2

- Any grade ≥ 3 pneumonitis
- Hematologic abnormalities
 - Neutropenia grade 4 despite holding duvelisib for 7 days
 - Thrombocytopenia grade ≥ 3 with bleeding
 - Thrombocytopenia grade 4
- Other immune-related toxicities
 - Any grade ≥ 3 toxicity that does not respond to treatment within 5d
- For the remainder of non-hematologic toxicities, grade ≥ 3

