12.1 Definitions

- **Evaluable for toxicity** – All patients are evaluable for toxicity upon initiating treatment of nivolumab and duvelisib. For the phase I portion, patients should have taken 75% of duvelisib pills according to pill diary and pill counts.
- **Evaluable for objective response** – Patients who have measurable disease at baseline and have their disease re-evaluated at 12 weeks of therapy will be evaluable for response. Patients who

exhibit objective disease progression prior to the end of cycle 1 will also be considered evaluable.

- **Evaluable non-target disease response** – Patients who have baseline lesions that are evaluable but do not meet the definitions of measurable disease have received at least one cycle of therapy and have had their disease re-evaluated will be considered evaluable for non-target disease. The response assessment is based on the presence, absence, or unequivocal progression of the lesions.
- **Measurable disease** – Tumor lesions that can be accurately measured by the longest diameter in the plane of measurement with a minimum size of 10mm by CT scan, 10mm caliper measurement on clinical exam, 20mm by chest x-ray. CT scan thickness should be no greater than 5mm. Tumor measurements must be recorded in mm or decimal fractions of centimeters.
- **Malignant lymph nodes** – To be considered pathologically enlarged and measurable, a lymph node must be $\geq 15\text{mm}$ in short axis when measured by CT scan. Only the short axis will be measured and followed.
- **Non-measurable disease** – All other lesions, including small lesions $< 10\text{mm}$ and lymph nodes $< 15\text{mm}$ are considered non-measurable disease. Other non-measurable disease examples include ascites, pleural or pericardial effusion, lymphangitic involvement of skin or lung, abdominal masses/abdominal organomegaly that don't correlate to CT or MRI, bone lesions, inflammatory breast disease.

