14.1. Phase I Portion of the Study

14.1.1. Study Design

The primary objectives of the phase I portion are to determine the maximum tolerated dose (MTD) of duvelisib when combined with anti-PD1 therapy nivolumab, and to decide on its recommended phase II dose (RP2D). Dose escalation will follow the decision rule in the following table, using the three dose levels defined in Section 7.5 (i.e., 15mg Daily, 25mg Daily, and 25mg BID), starting from the lowest dose. The MTD is defined to be the highest dose level at which no more than 1 of 6 treated patients experiences a DLT (DLT is defined in Section 8.1). Cohorts of three to six patients each will be treated at a dose level. Patients should have taken 75% of pills to be included in analysis of their respective cohort, as assessed through pill counts and pill diary. Only toxicities observed during the first treatment cycle will affect dose escalation. Late toxicities observed will be discussed at monthly data safety monitoring boards to determine if dose adjustments should be made.

After MTD is determined, we will decide on RP2D based on an overall consideration of DLT data, as well as immune cell profiling with laboratory correlates. For this purpose, our decision rule in the following table is a slight modification of the standard “3+3” to make sure 6 patients will be accrued at each safe dose in order to have enough patients for laboratory evaluations. RP2D should not be higher than MTD. If the MTD is not reached, RP2D will be decided based on safety data from acute and late toxicities as well as immune cell profiling data by the investigators (see section 13.1).

DECISION RULES FOR DOSE LEVEL ESCALATION

No. of patients with DLT's at this dose level	No. of patients treated at this dose level	Action
≤1	3	Treat 3 more patients at this dose level.
≤1	6	Treat 3 patients at the next higher dose level (or if at the highest level, stop the trial, and declare the dose at this level to be the MTD).

>1	3 or 6	Stop dose escalation. The previous dose is defined as MTD.
----	--------	--

Cohorts need not be completed if clear decisions can be made on the basis of an incomplete cohort. For example, if the first two patients in an intended cohort of three experience DLT's, escalation can be stopped without accruing the third member of the cohort.

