14.1.2. Sample Size/Accrual Rate

The number of patients accrued to the study will depend on the MTD. No more than 18 evaluable patients will be treated in the phase I portion. An evaluable patient is defined as one who either a) receives at least one dose the study drug and/or suffers DLT, or b) completes a treatment cycle and has no DLT observed during this cycle.

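### Read literally, section 8.1 leaves DLT-grade events in the optional 2-week duvelisib lead-in (7.5) out of the MTD count

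*Combined protocol and SAP*

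**What the plan says.** - **7.5 Treatment Regimen.** If significant toxicity (not defined further) is seen in the first three patients at a level, "subsequent patients may be treated with a 2 week lead-in of duvelisib as monotherapy prior to the addition of nivolumab".
- **8.1 Dose Limiting Toxicities.** Acute DLTs are treatment-related events that "occur any time from the initial dose of duvelisib in combination with nivolumab through day 28 of treatment". Late toxicities begin on day 29. "Only acute DLTs will be considered for decisions to continue enrollment at the current dose level or proceed to the next dose level".
- **14.1.1 Study Design.** This section takes its DLT definition from 8.1 and sets the MTD as the highest level with a DLT in at most 1 of 6 patients. It adds: "Only toxicities observed during the first treatment cycle will affect dose escalation". A patient must have taken 75% of the pills to be analysed with the cohort; 12.1 repeats this requirement for phase I.
- **12.1 Definitions.** "All patients are evaluable for toxicity upon initiating treatment of nivolumab and duvelisib".
- **14.1.2 Sample Size/Accrual Rate.** Under limb a), an evaluable patient is one who "receives at least one dose the study drug and/or suffers DLT".
- **4.4.1 Duration of Follow Up and Retreatment.** "The period of acute toxicity and DLT evaluation is 28 days". No starting day is given.

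No section extends the DLT window to the lead-in, says whether the lead-in belongs to cycle 1, or resets day 1 for lead-in patients.

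**The concern.** Duvelisib is the drug being escalated, and the lead-in is the one period in which a toxicity can be attributed to it without nivolumab in the picture. On the literal wording, a DLT-grade event in that period does not count towards the decision on the duvelisib dose.

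The lead-in is also reserved for levels where toxicity has already appeared. After 1 DLT in the first 3 patients, a single further counted DLT stops escalation. One uncounted lead-in event can therefore decide whether the level passes. In phase I the escalation count is the only fixed numerical rule; the other protections depend on judgement.

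**Working it through.** **Step 1. Where a lead-in event falls.** It precedes the first dose given with nivolumab, so it is before the acute window in 8.1. It also precedes day 29, so it is not a late toxicity. 14.1.1 imports the 8.1 definition, so the event is not in the 1-of-6 count. The start of toxicity evaluability in 12.1 (nivolumab and duvelisib both begun) points the same way.

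**Step 2. What happens to a patient who stops in the lead-in.** A 14-day lead-in covers at most 14/28 = 50% of a 4-week cycle's pills, below 75%. If cycle 1 starts with the combination, the share is 0%. The plan does not define the denominator, but on either 28-day basis the patient leaves the cohort analysis and the event goes with them. Limb a) of 14.1.2 conflicts with this, because one dose is enough there.

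**Step 3. Size.** The only phase I figure in the plan is the maximum size, which reproduces: 3 levels × 6 patients = 18. The plan gives no operating characteristics for the MTD rule, so what follows is an illustration.

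Inputs and assumptions:
- Rule (14.1.1): the level passes with at most 1 DLT in the first 3 and at most 1 in 6.
- p = true 28-day DLT rate on the combination, shown at 30% and 40%.
- m = 14-day risk of a DLT-grade event on duvelisib alone. The documents do not give it; 2%, 5% and 10% are shown.
- The lead-in is used for patients 4 to 6 only after exactly 1 DLT in the first 3. Lead-in and combination events are independent.
- A patient with an uncounted lead-in event is replaced or continues to the combination.

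Formula, with c the counted DLT rate in lead-in patients:

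Pass = P(0 of 3) × P(≤1 of 3) + P(1 of 3) × (1 − c)³

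- Lead-in events not counted: c = p.
- Lead-in events counted: c = 1 − (1 − m)(1 − p).

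At p = 30%, the first term is 0.343 × 0.784 = 0.2689 and P(1 of 3) = 0.441.
- Not counted: 0.2689 + 0.441 × 0.343 = 0.420.
- Counted: (1 − c)³ = 0.323, 0.294, 0.250 for m = 2%, 5%, 10%. Pass = 0.411, 0.399, 0.379.

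At p = 40%, the first term is 0.216 × 0.648 = 0.1400 and P(1 of 3) = 0.432.
- Not counted: 0.1400 + 0.432 × 0.216 = 0.233.
- Counted: pass = 0.228, 0.220, 0.208.

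| p | m | Pass, not counted | Pass, counted | Excess (points) |
|---|---|---|---|---|
| 30% | 2% | 0.420 | 0.411 | 0.9 |
| 30% | 5% | 0.420 | 0.399 | 2.2 |
| 30% | 10% | 0.420 | 0.379 | 4.1 |
| 40% | 2% | 0.233 | 0.228 | 0.5 |
| 40% | 5% | 0.233 | 0.220 | 1.3 |
| 40% | 10% | 0.233 | 0.208 | 2.5 |

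Conditional on 1 DLT in the first 3, at p = 30% and m = 5%, the level passes with probability 0.343 rather than 0.294. The chance that at least one of patients 4 to 6 has a lead-in event is 1 − (1 − m)³ = 0.059, 0.143 or 0.271.

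**The case against.** **The wording may name the regimen.** Duvelisib in combination with nivolumab is also how the protocol describes the study treatment, and the first treatment cycle in 14.1.1 could be taken to include the lead-in. On that reading lead-in events already count. The reading is possible, but no text adopts it and 12.1 points the other way. Two investigators could classify the same event differently under the escalation rule.

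**Counting combination events only is coherent.** The objective is the MTD of duvelisib when combined with nivolumab. Measured against the protocol's own 28-day combination rule there is no excess; the figures above compare it with a longer window, which will always count more. This stands as a description of the comparison. The plan does not say that it made this choice, however, and a DLT-grade event caused by the escalated drug bears on the dose.

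**The event risk is probably low.** Sections 11.1 to 11.4 put median onset of the main duvelisib toxicities at 3 to 4 months. Section 7.5 reports a monotherapy MTD of 75 mg BID in lymphoma, three times the top dose here. This stands, and favours the 2% end of the range.

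**Other safeguards exist.** Adverse events are collected from the start of treatment (5.2). The DSMB and DSMC can suspend accrual (10.1), and the RP2D may be set below the MTD (14.1.1). These limit the harm but do not correct the count.

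**Two stronger readings are tempting.** A reader of 14.1.2 might infer that a patient who stops in the lead-in fills one of the 6 places as DLT-free, which would enlarge the effect. The 75%-of-pills rule in 12.1 and 14.1.1 would normally exclude that patient, so the documents do not support this. A reader might also suppose that a quarter or more of all DLTs would fall in the lead-in; nothing in the documents supports such a share.

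**Conclusion.** The gap is real on the literal wording: a DLT-grade lead-in event belongs to neither toxicity window and is lost to the MTD count, and the evaluability rules disagree about a patient who stops there. Its effect is small and conditional. For an assumed m of 2% to 10%, the level passes 0.9 to 4.1 points too often at a 30% DLT rate and 0.5 to 2.5 points too often at 40%, relative to a window that counts lead-in events. That rests on an optional lead-in being used whenever exactly 1 of the first 3 patients has a DLT, and on a risk that the documents do not state and that is likelier at the low end. The length of the window is a lesser matter: 8.1, the 28-day period in 4.4.1 and the 4-week cycles in the Protocol Summary most naturally give 28 days from the first combination dose. Severity: minor.

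**What to change.** - In 8.1 and 14.1.1, state that for lead-in patients the DLT window runs from the first duvelisib dose through 28 days after the first nivolumab dose, and that escalation waits until it closes.
- In 12.1, 14.1.1 and 14.1.2, state that a DLT-grade event in the lead-in counts as a DLT and that the patient is evaluable whatever share of pills was taken. This also removes the conflict between 14.1.2 a) and the 75% rule for these patients.

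The cost is amendment wording, up to 2 more weeks before escalation when a lead-in is used, and a somewhat stricter window for lead-in patients (14 + 28 = 42 days against 28). If the sponsor prefers to count combination events only, the protocol should say so and state that a patient who stops before nivolumab does not fill a place; that may need a replacement patient. Whether to use a lead-in remains a clinical decision.

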	Moderate (Grade 2) symptomatic pneumonitis	
Duvelisib
 
 - Withhold duvelisib - Treat with systemic steroid therapy - If pneumonitis recovers to Grade 0 or 1, duvelisib may be resumed at reduced dose - If non-infectious pneumonitis recurs or patient does not respond to steroid therapy, discontinue duvelisib 
Nivolumab
 
 - Withhold nivolumab until resolved to grade 0-1 - Resume at same dose - Prednisone 1-2mg/kg/d, with long taper - Consider pulmonology consultation, bronchoscopy and biopsy, empiric antibiotics - Monitor closely, if no improvement in 2-3 days treat as grade 3
	Severe (Grade 3) or Grade 4 life-threatening pneumonitis	
Duvelisib
 
 - Discontinue duvelisib - Treat with systemic steroid therapy 
Nivolumab
 
 - Permanently discontinue nivolumab - Treat with high dose IV steroids, consider infliximab, empiric antibiotics - Pulmonary and infectious disease consultations and biopsy if able
ALT/AST elevation	3 to 5 x upper limit of normal (ULN) (Grade 2)	
Duvelisib
 
 - Maintain duvelisib dose - Monitor at least weekly until return to < 3 x ULN

Toxicity	Adverse Reaction Grade	Recommended Management
		
Nivolumab
 
 - Withhold nivolumab until resolved to grade 1 - Resume at same dose - Consider steroids if abnormality persists and clinical symptoms
	> 5 to 20 × ULN (Grade 3)	
Duvelisib
 
 - Withhold duvelisib and monitor at least weekly until return < 3 × ULN - Resume duvelisib at same dose (first occurrence) or at a reduced dose for subsequent occurrence 
Nivolumab
 
 - Permanently discontinue nivolumab - Start steroids with methylprednisolone at 1-2mg/kg/d - Consider liver biopsy
	> 20 × ULN (Grade 4)	
Duvelisib
 
 - Discontinue duvelisib - Systemic steroid treatment 
Nivolumab
 
 - Permanently discontinue nivolumab - Start steroids with methylprednisolone at 1-2mg/kg/d - Avoid infliximab - Hepatology consultation, consider liver biopsy
Hematologic Adverse Reactions		

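### Phase I counts a DLT-free patient toward the combination MTD on a duvelisib pill minimum alone; no number of nivolumab infusions is required beyond starting the drug

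*Combined protocol and SAP*

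**What the plan says.** Section 14.1.1 makes the MTD of duvelisib in combination with nivolumab a primary objective of phase I and defines it by a limit of 1 DLT among 6 treated patients. Only first-cycle toxicity drives escalation, and sections 4.4.1 and 8.1 set a 28-day acute window.

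On schedule, section 7.5 states "Nivolumab will be administered at a flat dose of 240mg every 2 weeks for the first 4 cycles". The Protocol Summary gives 4-week cycles for both drugs, and Table 6.7.1 lists cycle 1 visits on days 1 and 15.

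Three places say who counts:

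- Section 12.1: "All patients are evaluable for toxicity upon initiating treatment of nivolumab and duvelisib", followed by "For the phase I portion, patients should have taken 75% of duvelisib pills according to pill diary and pill counts".
- Section 14.1.1: "Patients should have taken 75% of pills to be included in analysis of their respective cohort".
- Section 14.1.2: "An evaluable patient is defined as one who either a) receives at least one dose the study drug and/or suffers DLT", or (limb b) one who finishes a treatment cycle without a DLT. What finishing a cycle means for nivolumab is not defined.

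For grade 2 ALT/AST elevation, Table 7.6 keeps the duvelisib dose unchanged and, for nivolumab, says "Withhold nivolumab until resolved to grade 1".

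**The concern.** A dose level is judged on six patients, and each one recorded as DLT-free is taken as evidence that the combination was tolerated. The authors recognised that under-dosed patients weaken that evidence, because they set a floor for duvelisib. They set none for the other study drug beyond its first dose.

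Table 7.6 supplies a route by which the two exposures separate. Grade 2 ALT/AST elevation is not on the DLT list in 8.1, where the residual non-hematologic category starts at grade 3. A withheld infusion is not a DLT either. Two other rows allow the same separation at the clinician's discretion: grade 1-2 diarrhea that responds to treatment, and an ANC of 500-1000 when nivolumab is thought to contribute.

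A patient on such a path can have full pill compliance and half the planned nivolumab, and still be scored DLT-free. The error runs one way, toward passing the level. The dose chosen in phase I is then given to the 24 further phase II patients.

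**Working it through.** **Plan's own figures.** Three levels × 6 = 18 phase I patients; 18 + 24 = 42 in total; 24 + 6 carried over = 30 in phase II. All reproduce.

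**Exposure in the window.** Infusions every 14 days from day 1 fall on days 1 and 15: 2 × 240 mg = 480 mg. If day 15 is withheld through day 28, the patient has 1 of 2 = 50%. Duvelisib can meanwhile be 28 of 28 capsules (daily) or 56 of 56 (BID), against minimums of 0.75 × 28 = 21 and 0.75 × 56 = 42. The patient passes the pill rule and satisfies limb (a) of 14.1.2.

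**Chance that a level passes.** Having at most 1 DLT in 6 implies at most 1 in the first 3, so the two-step rule reduces to P(q) = (1−q)^6 + 6q(1−q)^5, where q is the DLT probability per counted patient.

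The documents give no hold rate and no effect of a missed infusion, so both are assumptions. Let h be the share of patients with a persistent hold (0.10 or 0.20), and r the DLT risk without the second infusion relative to full exposure (0.75 or 0.5). Averaged over patients, q = p(1 − h + hr).

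At p = 0.40, which is above the 33% that section 8.1 calls acceptable:

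| h | r | q | P(at most 1 of 6) |
|---|---|---|---|
| 0 | – | 0.40 | 0.233 |
| 0.10 | 0.75 | 0.39 | 0.249 |
| 0.10 | 0.5 | 0.38 | 0.266 |
| 0.20 | 0.75 | 0.38 | 0.266 |
| 0.20 | 0.5 | 0.36 | 0.301 |

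For example, at q = 0.36: 0.64^6 + 6 × 0.36 × 0.64^5 = 0.069 + 0.232 = 0.301.

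**How often a cohort is touched.** P(at least one of 6 held) = 1 − (1−h)^6 = 0.47 at h = 0.10 and 0.74 at h = 0.20. At h = 0.10, two or more are held with probability 0.114 and three or more with probability 0.016.

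**Effect of replacing DLT-free held patients while always counting DLTs.** The counted DLT probability becomes q / [q + (1−h)(1−p)]. At p = 0.40, h = 0.10, r = 0.5 this is 0.38 / (0.38 + 0.54) = 0.413, and P = 0.214. At h = 0.20, r = 0.5 it is 0.36 / (0.36 + 0.48) = 0.429, and P = 0.192. Both are below 0.233, so the rule errs on the cautious side.

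**The case against.** **Removing patients who had toxicity could worsen the bias.** This is the strongest statistical objection, because held patients may be the more DLT-prone. Take an average risk of 0.33, with 20% held at a full-exposure risk of 0.66 and the rest at (0.33 − 0.2 × 0.66)/0.8 = 0.2475. Dropping every held patient gives a pass probability of 0.540, against 0.501 under current rules (risk halved by the hold) and 0.358 at full exposure. That result depends on discarding held patients who do have a DLT. If DLTs always count, q = 0.2 × 0.33 + 0.8 × 0.2475 = 0.264. The counted probability is 0.264 / (0.264 + 0.8 × 0.7525) = 0.305, and the pass probability is 0.410, an improvement on 0.501.

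**Holds that matter may be uncommon.** This stands in part. The hold must begin by about day 15 and last through day 28. Table 6.7.1 allows ±1 week, so a brief hold may still permit the infusion inside the window. Sections 11.1 to 11.4 give median onsets of 3 to 4 months for duvelisib infections, diarrhea/colitis, cutaneous reactions and pneumonitis. No onset is given for ALT/AST or for the combination. Of the three Table 7.6 rows, only grade 2 ALT/AST requires a nivolumab hold while duvelisib continues. A reader might infer that the gap arises in routine use; the documents do not show that.

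**Limb (b) may already cover it.** It can be read as requiring both infusions, but it is undefined, and limb (a) makes the patient evaluable regardless.

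**Other safeguards exist.** Late toxicity and immune profiling inform the RP2D, and 14.2.3.3 reports a 0.9128 stopping probability at a 40% toxicity rate in phase II. These limit the consequence but do not correct the phase I escalation count.

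**Nivolumab is a fixed background drug in pre-treated patients.** This is a fair reason to escalate only duvelisib. The MTD being declared is nevertheless that of the combination.

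**Conclusion.** The gap is real on the text: the quantitative minimum covers one of two study drugs, and the protocol's own management table can produce a DLT-free count on half the planned nivolumab. The direction is toward passing a level. The size is modest: at a true DLT rate of 40% the pass probability moves from 0.233 to 0.249-0.301, if 10-20% of patients are held and the missing infusion cuts risk by a quarter to a half. Those inputs are assumptions, so the range is illustrative.

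A reader might infer that an intolerable dose would often be passed, for instance by supposing three of six patients are under-exposed (0.415 at p = 0.40 with risk halved). At a 10% hold rate, three or more occurs with probability 0.016, so that is not the expected effect. Nor is passing a level at a true rate of 33% an error by the protocol's standard, since section 8.1 accepts that rate.

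Separately, limb (a) of 14.1.2 conflicts with the 75% rule in 12.1 and 14.1.1. Those sections need reconciling in any case.

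**What to change.** Replace the texts in 12.1, 14.1.1 and 14.1.2 with one definition:

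- A patient with a DLT always counts.
- A patient without a DLT counts toward the dose-level decision only after at least 75% of the duvelisib and all nivolumab infusions planned within the DLT window. A 75% floor on two infusions already means both, since one is 50%.
- Any other patient without a DLT is replaced for the escalation decision and stays in every safety table.

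Define the window from the first combination dose. Section 7.5 allows a 2-week duvelisib lead-in, and section 8.1 starts the window at the combination but ends it on day 28 of treatment. Under a lead-in, that could leave only one planned infusion inside it.

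State the totals of 18 and 42 in evaluable patients throughout. Section 14.1.2 does so for the 18, but the Protocol Summary and the opening of section 14.0 do not.

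The cost is protocol wording, occasional replacements (about 6 × 0.10 = 0.6 per level at a 10% hold rate) and a slightly conservative escalation rule. No dose or management rule changes.
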